RQ 2: Assess the effects of CGM implementation on nursing workload and factors influencing nursing care delivery. We examine nursing workload and care delivery factors through surveys administered to MICU nurses and through a MICU staff nurse focus group (N=10). *Nursing care delivery factors:* Acceptability of CGM measured by the Acceptability of Intervention Measure (AIM), appropriateness of CGM measured by the intervention appropriateness measure (IAM), and feasibility, measured by the Feasibility of Intervention Measure (FIM). Nursing care delivery factors, evaluation of CGM support, and CGM knowledge will be evaluated through focus groups and CGM Satisfaction Questionnaire (modified for healthcare workers). **Hypothesis:** The use of CGM will significantly reduce nursing workload while increasing frequency of glucose monitoring.

RQ 3: To assess glycemic control among patients receiving CGM in the CGM enabled MICU compared to historical control patients who received POC glucose monitoring in the MICU. Among critically ill patients on CGM (N=100) we will examine time in range (70-180mg/dl), time 100-180mg/dl, time 140-180mg/dl, time in hypoglycemia ($<55\text{mg/dl}$, $<70\text{mg/dl}$), and time in hyperglycemia (180-250mg/dl, $>250\text{mg/dl}$) compared to matched historical control patients using 3-tiered linear mixed models to control for patient, unit, and nurse specific variability. **Hypothesis:** Patients with CGM will exhibit greater time in range (100-180mg/dl, 140-180mg/dl, 70-180mg/dl) and experience less frequent time in hypoglycemia than patients on fingerstick POC.

RQ 4: (exploratory) To assess hospitalization outcomes and conduct economic evaluation of the costs to deliver CGM implementation in the MICU. We will track time and resources needed for CGM implementation including personnel, training, facilities, materials, equipment, and other necessary inputs. *Hospitalization outcomes criteria:* Length of stay [ICU, total stay], cost of stay, cost of CGM vs. standard POC glucose monitoring, discharge level of care [home, SNF], 30-day readmission, morbidity, and mortality. **Hypothesis:** Patients with CGM will experience shorter length of stay, lower cost of stay, will be more likely to discharge to home vs. SNF,

have lower 30-day readmission rate, and experience lower mortality/morbidity than matched historical control patients receiving fingerstick POC in the MICU.

II. Background and Rationale

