Sample Size Justification. The primary outcome for the power analysis is the percentage of time spent in target (70-180mg/dl). We estimate from previous studies^{13,28} that these values may have a standard deviation as high as 25 percentage points, in which case with 100 patients in each group we will have 80% power to detect a difference of 10 percentage points in time in range (e.g., 65 vs. 75); a moderate effect size of 0.4. If the standard deviation is lower (e.g., 15 as has been true in some studies), we will have greater power (99%) to detect a 10 point difference and are still well powered to detect smaller differences (e.g., 90% power for a 7 point difference). All power calculations assume an alpha of 0.05 and minimal statistical effects of clustering within the hospitals (e.g., unit or nurse level).

C. Detailed study procedures

Recruitment: Critical care clinical research coordinators will screen for preliminary eligibility and forward potential participant names to study team using a secure medical record in-basket process. The study team will determine eligibility. The study team will ask for permission for the patient to be approached. If permission is granted, the study team will verify eligibility and obtain informed consent from the patient or the patient's legally authorized representative. Consent will be obtained prior to research participation and CGM placement. Recruitment is expected at a rate of 5 patients per week over seven months. Our target recruitment will be 100 MICU patients.

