The patient will remain on CGM for the duration of their hospital stay and if discharged to home may transition to personal use of the Dexcom G6. The Dexcom G6 sensor is replaced every 10 days and will be removed and then replaced for some radiographic procedures or sensor failure. CGM data is automatically transferred to Dexcom's cloud-based Clarity system.

Table 3. OSUWMC Hypoglycemia Guideline, Patients Who are Not Alert, Are NPO, or on IV Insulin Infusion

Blood Glucose (BG) Level*	Action	Follow-Up
60-79 mg/dL	
 • Administer 7.5 g Dextrose D50% (15 ml) IV* • Consider calling House Officer if patient experiencing recurrent BG <70 mg/dL in past 12 h 	
 • Recheck BG q 15 min following treatment and treat accordingly until ≥ 80mg/dl • Once ≥ 80mg/dl, recheck BG q1h x2 (x4 if <45mg/dL at onset), then resume POC glucose as previously ordered, Patients who are admitted with hypoglycemia should be monitored at least q 4h for a minimum of 24h
45-59 mg/dL	
 • Administer 12.5 g Dextrose D50% (15 ml) IV* • Call House Officer to report BG and action taken 	
<45 mg/dL	
 • Administer 25 g Dextrose D50% (15 ml) IV* • Call House Officer to report BG and action taken 	
ALL	
 • Consider adding Dextrose 5% to maintenance IV fluids at a rate of ≥ 50ml/hr or increase rate of existing maintenance IV if dextrose source already present 	
 • If > 4h from initial event and BG ≥ 80mg/dl for two consecutive readings, may consider reducing IV dextrose

Variables and measures. *Clinical utility criteria:* Time to CGM validation within hybrid protocol parameters, mean percent of dosing decisions determined by CGM, changes in insulin dosing from standard guideline or outside standard times in response to alarm and/or trend data (as measured by manufacturer download data and corresponding EHR documentation). *Fidelity criteria:* Proportion of times CGM used non-adjunctively/number of

times non-adjunctive use indicated per protocol. *Adoption criteria:* Proportion of patients approached to received CGM monitoring/number of patients eligible to receive initial CGM monitoring.

RQ 2: To assess the degree to which CGM implementation within the ICU environment effects nursing workload and care delivery.

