Descriptive statistics of central tendency (range, mean, median, and standard deviation) will describe variable characteristics and examine data distribution for normality and outliers. Descriptive statistics will summarize the sample characteristics and distribution of each variable. Data will be screened for normality, outliers, and homogeneity. Continuous variables with normal distribution will be reported as mean (standard deviation) while non-normal distribution will be reported as median (interquartile range). For **RQ1**, multivariate linear models will be used to evaluate clinical utility and implementation variables while examining the effects of patient condition (i.e., sequential organ failure assessment (SOFA) score, renal replacement, ventilator support, pH) as covariates. For **RQ 2**, For qualitative analysis of focus group data, a code book will be developed a priori based on the semi-structured interview questions. Interview data, fieldnotes and memos were imported into NVivo 12.0 (Doncaster, Australia) for data management and analyzed using a qualitative descriptive approach.^{35,36} Two researchers ([name] and [name]) will perform qualitative analysis. Portions of text will be coded with terms that were low inference (“data close”); then grouped into thematic categories and subthemes.³⁵ For **RQ3**, hyperglycemic and hypoglycemic events will be identified for CGM and non-CGM users. Discrete CGM glucose values will be used to aggregate derived measures of glucose variability, including time in target (blood glucose value of 70-180mg/dl), time 100-180mg/dl (representing a more conservative target used inpatient), time 140-180mg/dl (representing institutions IV insulin guideline glycemic target), time above target (>180mg/dl & >250mg/dl), time in hypoglycemia (<70mg/dl & <55mg/dl), glucose standard deviation, and coefficient of variation. Daily percent time in target as well as cumulative time in target will be assessed. Time in target will be derived from ADA glucose targets defining hypoglycemia as a blood glucose less than 70mg/dl and peak post-prandial glucose as <180mg/dl³⁷. The blood glucose range of 70-180mg/dl is consistent with other studies examining time in target.³⁸⁻⁴¹ Measures of hypoglycemia will be in accordance with ADA recommendations for measurement at <70mg/dl and <55mg/dl which is a marker of severe hypoglycemia.⁴² Days with $\geq 70\%$ CGM percent wear, as recommended by ADA, will be included in daily time in target analysis.⁴² For matched historical control patients, percent POC in target (70-180mg/dl), 100-180mg/dl, 140-180mg/dl, percent POC >180mg/dl and percent POC >250mg/dl, percent POC <70mg/dl and percent POC <55mg/dl will be evaluated consistent with other recent studies.^{43,44} For CGM daily glycemic control (i.e., time in range [70-180mg/dl], time 100-180mg/dl, time 140-180mg/dl), linear mixed effect modeling (LMM) for repeated measures will be used to adjust for between subject and within subject variance. A 3-tiered LMM will be used to control for patient, unit, and nurse specific variability. LMM will be repeated for analysis of daily POC glucose control for matched historical control patients for days with ≥ 3 POC fingersticks performed. Two-sided significance level of 0.05 was used for all the statistical tests. For **RQ4**, the cost analysis for the proposed study will be conducted from the provider perspective. Cost estimation involves three major steps: (1) identify the relevant cost items; (2) measure the use of resources; and (3) place a value on the resources used. We will obtain estimated costs for proposed CGM implementation. Direct benefits and savings tend to fall into one of two categories: either savings from enhanced efficiency and productivity, or savings from outcomes improvement (e.g., reducing length of stay, lower 30 day readmissions). Costs that do not vary with the number of patients will be categorized as fixed costs, whereas those that vary by the number of patients will be defined as variable costs. The costs of the CGM implementation will be compared to costs under a control scenario. We will estimate the potential costs and cost savings resulting from the CGM implementation.

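### RQ3 hypoglycemia is measured as time on CGM in one arm and as a share of POC readings in the other, and the plan does not settle how the two are compared

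*Combined protocol and SAP*

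**What the plan says.** RQ3 in section I (Objectives) lists time below 55 and below 70 mg/dl among the outcomes to be compared with matched historical controls "using 3-tiered linear mixed models to control for patient, unit, and nurse specific variability". Its hypothesis has two halves: more time in range and less hypoglycemia.

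Table 2 (Patient Participant Schedule of Activities) and section III.D (Data Analysis) define hypoglycemia as time below threshold for CGM patients. For controls, "percent POC <70mg/dl and percent POC <55mg/dl will be evaluated consistent with other recent studies". CGM days need at least 70% wear to enter the daily time-in-target analysis; control days need at least three POC readings.

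Section III.D names the mixed model for the three in-range measures only and says it is repeated for the controls. It says hypoglycemic events will be identified in both groups but names no test for them. Normality is screened, and the stated consequence of non-normality is reporting a median and interquartile range.

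Table 3 (OSUWMC Hypoglycemia Guideline) says "Recheck BG q 15 min following treatment and treat accordingly" until 80 mg/dl or above, followed by hourly checks. In the Sample Size Justification, "The primary outcome for the power analysis is the percentage of time spent in target (70-180mg/dl"). No hypoglycemia outcome is powered.

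**The concern.** There are three linked problems.

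- **Different quantities.** A share of clock time and a share of readings agree on average only if readings are taken without regard to glucose. After a low, the site's guideline makes reading times depend on glucose.
- **Unsuitable error model.** The outcome is bounded at zero, close to zero, and analysed by day. A normal-error model describes such data poorly, and a few patients or days can drive the estimate.
- **Unsettled analysis.** On the Objectives text, hypoglycemia gets a linear mixed model. On the Data Analysis text, it has no between-group analysis.

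At stake is half of the RQ3 hypothesis. A reported reduction or increase could reflect the measurement method, and the choice of test would be left until after the data are seen.

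**Working it through.** **1. The plan's own power figures.** Inputs from the Sample Size Justification: 100 per group, SD 25 or 15, alpha 0.05; two-sided per Data Analysis. SE = SD × √(2/100); power = Φ(δ/SE − 1.96).

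- δ 10, SD 25: SE 3.536; Φ(2.828 − 1.960) = 80.7% (stated 80%).
- δ 10, SD 15: SE 2.121; Φ(4.714 − 1.960) = 99.7% (stated 99%).
- δ 7, SD 15: Φ(3.300 − 1.960) = 91.0% (stated 90%).

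All three reproduce. They concern time in range only.

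**2. Shape.** Time below 70 mg/dl in the site's 19 COVID-19 CGM patients (section II) was 1.5±4.1% on day 1 and 0.16±0.35% on days 2-7. SD/mean is 2.7 and 2.2. A normal distribution with these moments would put Φ(−1.5/4.1) = 36% and Φ(−0.16/0.35) = 32% of values below zero, where none can lie.

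**3. Zeros.**

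- CGM arm: 0.16% of 288 readings is 0.46 readings a day (0.0016 × 1440 = 2.3 minutes). A non-zero day holds at least one reading. If 0.16% is an average over days, at most 46% of days are non-zero.
- Control arm, with readings unrelated to glucose and independent: at 0.16% true time, the chance that a day shows no low is 0.9984³ = 99.5% with three readings and 0.9984⁶ = 99.0% with six. At 1.5% it is 0.985³ = 95.6% and 0.985⁶ = 91.3%.

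**4. Step size.** One low reading is 1/288 = 0.35% of a CGM day and 1/3 = 33% of a control day at the minimum. With six readings (an assumed frequency; the plan gives only the minimum) it is 1/6 = 17%.

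**5. Identical glucose, different result.** Assume one low per day at a random time, six evenly spaced POC readings, the Table 3 rechecks (every 15 minutes until recovered, then two hourly), direct recovery to 80 or above, and no effect of treatment on duration.

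- Without rechecks, the expected daily percentage equals true time: for a 20-minute low, (20/240) × (1/6) = 1.39% = 20/1440. The coarse step alone does not shift the mean.
- 20-minute low with rechecks: detected with probability 1/12. Then 1 low of 9 readings (probability 0.75) or 2 of 10 (0.25), average 13.3%. Mean daily value 13.3%/12 = **1.1%, against 1.4% true**.
- 60-minute low: detected with probability 0.25. Then 1/9, 2/10, 3/11 or 4/12 with equal probability, average 22.9%. Mean daily value **5.7%, against 4.2% true** (60/1440).
- Pooling readings instead of averaging days, 20-minute low: expected lows 1.25/12 = 0.104, expected readings 6 + 3.25/12 = 6.27, giving 1.7% against 1.4%.

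The sign changes with the length of the low and with the averaging rule.

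**6. What can be said on power.** With the section II SDs and 100 per group, the difference detectable at 80% is 2.802 × SD × 0.1414: 1.62 points for day 1 (108% of the mean) and 0.139 points for days 2-7 (87% of the mean). If the control mean is 1.25 to 5 times the CGM mean at a constant SD/mean ratio, power runs from about 8% to 95%. The documents give no control rate, control SD or target difference with which to choose within that range.

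**The case against.** Several points on the other side stand.

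- A reader might infer that the linear comparison has poor power and that comparing the proportion with any event would be better. The documents do not support this. In simulation with 100 per group and the section II moments (days 2-7 / day 1), cutting incidence from 40% to 20% gives a two-sample t-test 52% / 41% power against 88-89% for any event. Keeping incidence at 40% and halving duration gives the t-test 59% / 42% and any event about 5-6%. The ranking depends on whether CGM changes incidence or duration, and shorter lows are plausible with alarms that nurses act on.
- A reader might infer that skew invalidates the test. With 30-70% zeros assumed and 100 per group, simulated t-test type I error was 4.3-5.8%. The objection to the model is fit and interpretation, not gross invalidity.
- A reader might infer that rechecks always inflate the control percentage. Recovered rechecks dilute it: 1/6 = 17% becomes 1/9 = 11%. Table 3 also covers only patients who are not alert, are NPO or are on IV insulin.
- The mismatch of units comes from the measurement methods, not from the mixed model, and it affects time in range too.
- Safety does not rest on this analysis; the pilot benchmarks and stopping criteria count episodes separately.
- The section II figures come from 19 patients with COVID-19, an exclusion here, and describe CGM wearers only.

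None of this supplies a common unit or a named test. Identifying events in both groups is a start, but no comparison follows from it.

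**Conclusion.** The point holds as one of comparability and specification. Followed as the Objectives state it, RQ3 compares percent of time with percent of partly outcome-triggered readings. It does so with a normal-error daily model, on an outcome whose daily values are likely to be mostly zero. In the illustration, identical glucose gives control values of 1.1% against 1.4%, or 5.7% against 4.2%, so neither direction of error can be presumed. The Objectives and Data Analysis must be reconciled, because only the former assigns hypoglycemia to the model.

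Hypoglycemia is unpowered. Neither poor power nor an advantage for any-event analysis is established.

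This rests on the site's earlier CGM figures being roughly indicative of the new patients, on Table 3 having applied to the controls' stays, and on the POC schedule assumed in the illustration. The difference in units does not depend on any of these.

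**What to change.** State one between-group hypoglycemia analysis and use it in both the Objectives and Data Analysis:

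- Derive it from POC readings in both arms, during MICU days only. Collapse a low reading and its rechecks into one episode.
- Analyse episodes below 70 and below 55 mg/dl per MICU patient-day with a negative binomial model, an offset for exposure and clustering by matched set. Give any value below 70 and any below 55 per patient as supporting analyses.
- Report POC tests per day by arm. Table 1 (Initial and Ongoing CGM Validation) varies POC frequency in the CGM arm and adds tests after low alerts, CGM lows and predicted lows. Controls had no such triggers.
- Add a sensitivity analysis on a common schedule, for example one scheduled reading per 4 hours in both arms, leaving out alert-triggered and recheck readings. This selects readings for analysis and changes no testing or care.
- Report CGM time below 70 and below 55 as median (IQR) in the CGM arm only.
- State that hypoglycemia is unpowered.

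The cost is SAP wording and a derivation rule using POC time stamps and Clarity alarm records; no new data are needed. The downside is that POC misses some lows that CGM detects. Some difference in detection between arms will also remain, and the report should say so.
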